### Primary Safety Endpoints:

- Fatal and non-fatal major bleeding using the International Society on Thrombosis and Haemostasis (ISTH) bleeding criteria

### Secondary Safety Endpoints:

- Clinically relevant non-major bleeding
- Non-major bleeding that lead to study-drug interruption for more than 7 days

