The dosage of the study medication will be adjusted upon hospital discharge of the patients as follows. Patients randomized to rivaroxaban 20 mg OD will reduce daily dosage to 10 mg OD, provided that they were not diagnosed with a condition requiring continued therapeutic anticoagulation.

Patients randomized to the SOC arm will receive SOC with prophylactic LMWH or UFH according to local practice, provided that they were not diagnosed with a condition requiring continued therapeutic anticoagulation. Study visits are terminated 7, 35, and 60 days post randomization. The 60 day EOS visit will be done as a telephone visit.

If a subject has a suspected efficacy or bleeding outcome event during the study, the treating physician should clinically judge and follow established guidelines to apply best medical care.

The primary endpoint is to assess the effect of rivaroxaban compared with standard of care (SOC) with the use of prophylactic low molecular weight heparin (LMWH) or unfractionated heparin (UFH) on D-dimer as a clinical marker for a worse clinical outcome at day 7 post randomization adjusted for baseline measurement in patients with moderate to severe COVID-19.

The co-primary endpoint is to evaluate the impact of rivaroxaban compared with standard of care (SOC) with the use of prophylactic low molecular weight heparin (LMWH) or unfractionated heparin (UFH) on a seven-category ordinal scale recommended by the WHO as a measure of clinical benefit at day 7 post randomization in patients with moderate to severe COVID-19.

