## Safety Objectives

The safety objectives are to compare rivaroxaban with SOC with prophylactic LMWH or UFH in bleeding outcomes up to day 35 in patients with moderate to severe COVID-19.

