In case of hospitalization for more than 7 days, the therapeutic treatment with rivaroxaban will be continued for the duration of the hospital stay until discharge. After at least 7 days of therapeutic treatment with rivaroxaban or after hospital discharge, whatever is the event that occurs later, the study dose of rivaroxaban will be adjusted as follows: Patients randomized to rivaroxaban 20mg OD will reduce daily dosage to 10 mg OD, provided that they were not diagnosed with a condition requiring continued therapeutic anticoagulation. Thromboprophylaxis therapy will be given for 28 days up to day 35 post randomization or even longer. If the patient cannot be discharged from the hospital prior to day 35 post randomization, the thromboprophylaxis phase will also start upon hospital discharge, but is then shorter than 28 days, because the study ends latest at day 60 post randomization. The complete end of study (EOS) visit will be done via phone call 60 days post randomization. No study medication will be given thereafter.

After the study, the patients continue to receive medical therapy according to local practice.

If the clinical condition of a hospitalized patient deteriorates and admission to ICU with possible invasive ventilation will become necessary, treatment with rivaroxaban should be discontinued for the ICU period and the patient switched to parental or subcutaneous anticoagulation following best local practice. After clinical improvement and discontinuation of invasive ventilation, the anticoagulation mentioned above can be replaced by study drug rivaroxaban 20 mg OD (15 mg for subjects with an  $eGFR \geq 30$  mL/min/1.73m^2 and <50 mL/min/1.73m^2) at the discretion of the clinically responsible physician.

Patients randomized to the SOC treatment arm will receive SOC during the time of hospitalization or for at least 7 days, whatever is later. SOC constitutes of prophylactic doses of LMWH or UFH, according to the local practice and decision of the physicians of the respective trial site. Study visits are terminated 7, 35, and 60 days post randomization in all patients. The latter will be done via phone call if applicable. For the hospitalized patients who are discharged later than 10 days post randomization, an additional discharge visit will be done at the day of discharge (-2 days).

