### **9.3. Safety Evaluations and Endpoints**

#### **9.3.1. Bleeding Events**

The study will include the following evaluations of safety and tolerability according to the time points provided in the TIME AND EVENTS SCHEDULE: ISTH fatal or non-fatal major bleeding, non-major clinically relevant bleeding, other non-major bleeding that lead to study drug interruption for more than 7 days, adverse events, and clinical laboratory tests.

The study will use the ISTH Bleeding Event Classification Scale to assess bleeding events as major, non-major clinically relevant bleeding, or other bleeding. Similar to efficacy endpoint, the same independent CEC will adjudicate and classify bleeding events according to definitions in the CEC charter.

The principal safety endpoint for this study is fatal or non-fatal major bleeding using validated ISTH bleeding criteria (27). Other safety endpoints are non-major clinically relevant bleeding and non-major bleeding that lead to study drug interruption for more than 7 days.

An ISTH major bleeding event is defined as overt bleeding that is associated with:

- A fall in hemoglobin of 2 g/dL or more, or
- A transfusion of 2 or more units of packed red blood cells or whole blood, or
- A critical site: intracranial, intraspinal, intraocular, pericardial, intra-articular, intramuscular with compartment syndrome, retroperitoneal, or
- A fatal outcome

Non-major clinically relevant bleeding is defined as overt bleeding not meeting the criteria for major bleeding but associated with medical intervention, unscheduled contact (visit or telephone call) with a physician, (temporary) cessation of study treatment, or associated with discomfort for the subject such as pain or impairment of activities of daily life. Examples of non-major clinically relevant bleeding are:

- Epistaxis if it lasts for more than 5 minutes, if it is repetitive (i.e. 2 or more episodes of true bleeding, i.e. not spots on a handkerchief, within 24 hours), or leads to an intervention (packing, electrocautery, etc.)
- Gingival bleeding if it occurs spontaneously (i.e. unrelated to tooth brushing or eating), or if it lasts for more than 5 minutes
- Hematuria if it is macroscopic, and either spontaneous or lasts for more than 24 hours after instrumentation (e.g. catheter placement or surgery) of the urogenital tract
- Macroscopic gastrointestinal hemorrhage: at least 1 episode of melena or hematemesis, if clinically apparent

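### The bleeding endpoint defined by study-drug interruption of more than 7 days depends on how much assigned treatment remains, which differs by arm, so its comparison is biased against rivaroxaban by construction

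*Protocol*

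**What the plan says.** The safety objective (synopsis and section 2.1) is to compare rivaroxaban with SOC "in bleeding outcomes up to day 35 in patients with moderate to severe COVID-19". The principal endpoint is ISTH major bleeding. The two secondary endpoints are clinically relevant non-major bleeding and "Non-major bleeding that lead to study-drug interruption for more than 7 days". The second of these recurs in the synopsis and in section 9.3.1.

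Assigned treatment length differs between the arms:

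- **Rivaroxaban (section 3.1):** at least 7 days at the therapeutic dose, extended to discharge if that is later. After that, "Thromboprophylaxis therapy will be given for 28 days up to day 35 post randomization or even longer".
- **SOC (section 3.1, repeated in the Figure 1 legend):** "Patients randomized to the SOC treatment arm will receive SOC during the time of hospitalization or for at least 7 days, whatever is later".
- **SOC in the synopsis, in the part on adjustment at discharge:** "Patients randomized to the SOC arm will receive SOC with prophylactic LMWH or UFH according to local practice". This sets no end date.

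Section 11.5 plans a Cox model for time to the bleeding events of section 9.3.1, if there are enough events, with hazard ratios and p-values. It does not exempt the interruption endpoint.

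The term study drug is not used consistently. Section 14.1 calls LMWH or UFH the study drug of the second arm. Section 6 equates study drug with rivaroxaban and sets its first dose against the last dose of heparin. Section 10.2.1 also names study drug and SOC treatment as alternatives.

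**The concern.** An endpoint that requires more than 7 days off drug can be met only while enough drug is still assigned. Where SOC has ended, or has 7 days or fewer to run, a non-major bleed cannot meet it. The same bleed on the same day in a rivaroxaban patient can. Part of any difference would then reflect the length of the assigned course and not bleeding.

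This is separate from the extra bleeding that longer anticoagulation may cause, which is a genuine effect of the strategy. The artefact is that equal bleeds are counted unequally. Central adjudication of the bleed does not remove it, because the unequal part is the drug criterion. The trial is also open label (section 5), so the decision to interrupt is made knowing the arm. At stake is a definitional difference being reported as a rivaroxaban bleeding signal.

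**Working it through.** The protocol gives no expected rate or precision for this endpoint, so there is no stated figure to reproduce. The check is of the onset window.

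**Inputs**

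- Interruption threshold: more than 7 days (section 2.1).
- Rivaroxaban course: at least 7 + 28 = 35 days (section 3.1).
- SOC course T: minimum 7 days (section 3.1). Longer values are assumptions.
- Comparison horizon: day 35 (section 2.1).
- Interruption is taken to mean withholding of assigned doses. The protocol does not define it.

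**Step 1: onset window.** A bleed on day t can lead to an interruption of more than 7 days only if T − t > 7. The window is w = max(0, T − 7) days, give or take a day for the counting convention. For rivaroxaban at its minimum course, w = 35 − 7 = 28. For SOC at the minimum, w = 7 − 7 = 0.

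**Step 2: apparent risk with no true difference.** Assume the same hazard h per day within the window in both arms, and a 5% risk on rivaroxaban over its 28 days (an illustrative value). Then h = −ln(0.95)/28, and the SOC risk is 1 − exp(−h·w) = 1 − 0.95^(w/28). For T = 14 this is 1 − 0.95^(7/28) = 1.27%, and the ratio is 5/1.27 = 3.9. Expected events are per 50 patients, since section 11.7 aims for about 100 in total.

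| SOC course T (days) | SOC window w (days) | Share of 28 days | SOC risk | Rivaroxaban:SOC risk ratio | Expected SOC events per 50 |
|---|---|---|---|---|---|
| 7 | 0 | 0% | 0% | infinite | 0 |
| 10 | 3 | 11% | 0.55% | 9.1 | 0.27 |
| 14 | 7 | 25% | 1.27% | 3.9 | 0.64 |
| 21 | 14 | 50% | 2.53% | 2.0 | 1.27 |
| 35 | 28 | 100% | 5% | 1.0 | 2.5 |

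Rivaroxaban has 50 × 0.05 = 2.5 expected events in every row.

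**Step 3: sensitivity to the assumed risk.** With 10% on rivaroxaban, the ratios for T = 10, 14, 21 and 35 are 8.9, 3.85, 1.95 and 1.0. The ratio depends almost entirely on the windows.

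**Step 4: direction of the simplification.** The 28-day window is rivaroxaban's smallest. A rivaroxaban patient with a 14-day stay is assigned 14 + 28 = 42 days, giving a window of 42 − 7 = 35 days against 7 for a SOC patient with the same stay. Comparing equal stays would widen the gap.

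**Step 5: meaning of study drug.** If heparin counts (section 14.1), the table applies. If study drug means rivaroxaban only (section 6), the SOC window is 0 for every T.

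**The case against.** A reader might infer that the event cannot occur under SOC and that the comparison can only go against rivaroxaban. The documents do not support that. Seven days is a minimum and not a cap, SOC lasts for the whole hospital stay, and the synopsis leaves it to local practice. Section 14.1 counts heparin as study drug. SOC patients treated beyond about 8 days can have the event, and a higher SOC count is unlikely but possible. Without a length of stay, the share of SOC patients with no window is unknown.

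A reader might also infer that clinically relevant non-major bleeding is compromised in the same way, because temporary cessation of study treatment is among its criteria (section 9.3.1). That does not follow. Cessation is one of several alternatives, beside medical intervention, unscheduled physician contact and discomfort, and the listed examples do not depend on treatment. Section 9.1.3 tells subjects in either arm to seek medical attention for bleeding, so most such bleeds would qualify by another route. Only bleeds that qualify solely through cessation are affected, and nothing shows that these are many. ISTH major bleeding does not involve interruption at all.

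Finally, the study is exploratory, the Cox model is conditional on enough events, and longer rivaroxaban treatment is part of the strategy under test. All of this stands and limits the consequence. It does not remove the artefact: event frequencies by arm would carry the same imbalance even if no model were fitted.

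**Conclusion.** The point holds for the interruption endpoint alone. Its between-arm comparison is biased against rivaroxaban by construction. A SOC patient on the 7-day minimum cannot have the event. For assumed SOC courses of 10, 14 and 21 days, the apparent risk ratio with no true difference is about 9, 4 and 2. The bias vanishes only if SOC matches the rivaroxaban course to day 35.

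The size rests on three assumptions: the SOC duration, an equal hazard per day within the window, and interruption meaning that assigned doses are withheld. The direction does not depend on the assumed 5% risk. The conflict between sections 6 and 14.1 decides whether SOC patients can score at all, and the text leaves it open. The principal safety endpoint is unaffected, so this is a matter to correct before analysis and not a threat to the trial's main safety conclusion.

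**What to change.** 1. Reconcile sections 6 and 14.1 so that study drug and interruption mean the same in both arms. State how an interruption is counted under SOC and after the planned SOC course has ended.
2. Report this endpoint descriptively in both arms, with days at risk (days on which more than 7 assigned days remain). Exclude it from the hazard ratios and p-values of section 11.5. Reporting it for rivaroxaban only would discard valid SOC events.
3. Alternatively, restrict any comparison to the common treatment period. This has a limit: for SOC patients on the 7-day minimum, the common period is 7 days and no qualifying interruption fits in it.
4. Base between-arm bleeding inference on ISTH major and clinically relevant non-major bleeding, with their definitions unchanged. As a sensitivity check only, flag clinically relevant non-major bleeds that qualify solely through cessation of study treatment.

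The cost is wording in sections 2.1, 6, 9.3.1, 11.5 and 14.1, plus one flag on adjudicated bleeds. The amendment rationale reports 111 patients randomized and no further recruitment planned, so trial conduct need not change. The downside is that one comparative secondary safety endpoint becomes descriptive.

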### Other endpoints of interest:

- Length of hospital stay
- Time to intubation
- Re-hospitalization due to heart failure
- Re-hospitalization due to any other reason
- Effects on coagulation parameters for thrombosis (TAT, PAI-1, PF-4, TF, TF-activity)
- Effects on inflammatory and fibrotic parameters (interleukines, interferons, growth factors)
- Change of N-terminal prohormone brain natriuretic peptide (NT-pro-BNP)
- Unscheduled outpatient visits

## 2.2 Hypotheses

The primary hypothesis is that rivaroxaban but not SOC with prophylactic LMWH or UFH is effective in the reducing D-dimer at day 7 post randomization compared to baseline in patients with moderate to severe COVID-19. The co-primary hypothesis is that rivaroxaban compared to SOC with prophylactic

LMWH or UFH is superior to improve the patients' categories on a seven-category ordinal scale for patients with respiratory infections at day 7 post randomization.

The secondary hypothesis is that therapeutic anticoagulation with rivaroxaban for at least 7 days, followed by prophylactic anticoagulation with rivaroxaban for 28 days is superior to SOC with prophylactic LMWH or UFH in the prevention of the composite of VTE (DVT and/or fatal or non-fatal PE), arterial thromboembolism, new MI, non-hemorrhagic stroke, all-cause death and progression to intubation and invasive ventilation up to day 35 post randomization in patients with moderate to severe COVID-19.

### 3. STUDY DESIGN AND RATIONALE

#### 3.1 Overview Study Design

This is a multicenter, prospective, randomized, event-driven phase II study designed to assess the effect of therapeutic anticoagulation with high dose rivaroxaban intended for at least 7 days compared with SOC with prophylactic LMWH or UFH on the clinical prognosis marker D-dimer at day 7 post randomization adjusted for baseline measurement in patients with moderate to severe COVID-19. Moreover, this study investigates the effect of therapeutic anticoagulation with rivaroxaban compared with SOC with prophylactic LMWH or UFH on a seven-category ordinal scale for patients with respiratory infections at day 7 post randomization adjusted for baseline score.

Secondarily, this trial is designed to evaluate therapeutic anticoagulation with rivaroxaban for at least 7 days followed by thromboprophylaxis with rivaroxaban for 28 days, as compared with SOC with prophylactic LMWH or UFH in the prevention of the composite of VTE (DVT and/or fatal or non-fatal PE), arterial thromboembolism, new MI, non-hemorrhagic stroke, all-cause death and progression to intubation and invasive ventilation up to day 35 post randomization in patients with moderate to severe COVID-19. The study consists of a screening phase, a therapeutic treatment phase of at least 7 days and a thromboprophylaxis phase up to day 35 post randomization. The physicians of the respective trial site decide which heparin, of the heparins approved in Germany, the patients assigned to treatment group "SOC with prophylactic UFH or LMWH" will receive.

The subject population comprises men and women aged 18 years and older who have been tested positive for SARS-CoV-2 and who have moderate to severe COVID-19.

In order to be eligible, all patients must exhibit at least one of the following conditions:

- D-dimer elevation > 1.5 ULN (using age-adjusted cut-offs) and/or
- Cardiac injury reflected by an elevation in hs-cTnT > 2.0 ULN and one of the following conditions:
  - Known CAD
  - Known diabetes mellitus
  - Active smoking

The inclusion of D-dimer negative patients with cardiac injury reflected by an elevation in hs-cTnT > 2.0 ULN and one of the following conditions, known CAD or known diabetes mellitus or active smoking, will be limited to 15 % of the patients included in the study.

85% or more of the patients enrolled should be enrolled due to increased D-dimer defined as:

- D-Dimer elevation above 750 µg/L in patients 50 years of age or younger.
- In patients older than 50 years an age-adjusted cut-off will be calculated using the following formula:  $15 \times \text{Age } \mu\text{g/L}$ .

Any patient with a medical condition that requires use of any therapeutic parenteral or therapeutic oral dose anticoagulation (e.g. atrial fibrillation) is not eligible for participation. Moreover, patients at particularly increased risk of bleeding and those using medications that might interact with the study drug will be excluded.

Subjects with moderate to severe respiratory symptoms, tested positive for SARS-CoV-2, can be enrolled into the study, if the subjects meet all of the inclusion and none of the exclusion criteria. The

subjects will be randomly assigned to receive treatment with rivaroxaban or SOC with prophylactic LMWH or UFH.

Randomization can occur during the hospital stay or out-of-hospital, if admission to the hospital is not necessary, whatever the treating physician judges. Randomization should not occur later than 3 days after screening. Subjects will be randomized by strata including site, gender (male, female, diverse), age (< 65 versus  $\geq 65$  years), kidney function ( $eGFR \geq 30$  mL/min/1.73m^2 and < 50 mL/min/1.73m^2 versus  $eGFR \geq 50$  mL/min/1.73m^2), history of CAD or heart failure (yes/no), oxygen demand on admission to the hospital (supplementary oxygen required versus not required) and setting (outpatients versus hospitalized patients).

After randomization, subjects will receive treatment with rivaroxaban 20 mg (15 mg for subjects with an  $eGFR \geq 30$  mL/min/1.73m^2 and <50 mL/min/1.73m^2) once daily (OD) for at least 7 days or SOC with prophylactic LMWH or UFH according to the local standards and choice of the treating physician.

In case of hospitalization for more than 7 days, the therapeutic treatment with rivaroxaban will be continued for the duration of the hospital stay until discharge. After at least 7 days of therapeutic treatment with rivaroxaban or after hospital discharge, whatever is the event that occurs later, the study dose of rivaroxaban will be adjusted as follows: Patients randomized to rivaroxaban 20mg OD will reduce daily dosage to 10 mg OD, provided that they were not diagnosed with a condition requiring continued therapeutic anticoagulation. Thromboprophylaxis therapy will be given for 28 days up to day 35 post randomization or even longer. If the patient cannot be discharged from the hospital prior to day 35 post randomization, the thromboprophylaxis phase will also start upon hospital discharge, but is then shorter than 28 days, because the study ends latest at day 60 post randomization. The complete end of study (EOS) visit will be done via phone call 60 days post randomization. No study medication will be given thereafter.

After the study, the patients continue to receive medical therapy according to local practice.

If the clinical condition of a hospitalized patient deteriorates and admission to ICU with possible invasive ventilation will become necessary, treatment with rivaroxaban should be discontinued for the ICU period and the patient switched to parental or subcutaneous anticoagulation following best local practice. After clinical improvement and discontinuation of invasive ventilation, the anticoagulation mentioned above can be replaced by study drug rivaroxaban 20 mg OD (15 mg for subjects with an  $eGFR \geq 30$  mL/min/1.73m^2 and <50 mL/min/1.73m^2) at the discretion of the clinically responsible physician.

Patients randomized to the SOC treatment arm will receive SOC during the time of hospitalization or for at least 7 days, whatever is later. SOC constitutes of prophylactic doses of LMWH or UFH, according to the local practice and decision of the physicians of the respective trial site. Study visits are terminated 7, 35, and 60 days post randomization in all patients. The latter will be done via phone call if applicable. For the hospitalized patients who are discharged later than 10 days post randomization, an additional discharge visit will be done at the day of discharge (-2 days).

If the treating physician switches a patient in the SOC treatment group from prophylactic to therapeutic anticoagulation, a medically evidence-based reason must be given. All changes of anticoagulation must be properly documented in the eCRF.

The first dose of the study drug should be administered as soon as possible and no later than the day after the subject is randomized. Subjects and medical personal in charge of the administration of the drugs will be instructed how to administer the drug.

If a subject has a suspected efficacy or bleeding outcome event during the study, the treating physician should exercise clinical judgment and follow established guidelines.

The primary objective is to assess the effect of rivaroxaban compared with standard of care (SOC) with the use of prophylactic low molecular weight heparin (LMWH) or unfractionated heparin (UFH) on D-dimer as a clinical marker for the clinical outcome at day 7 post randomization adjusted for baseline measurement in patients with moderate to severe COVID-19.

The co-primary objective is to evaluate the impact of rivaroxaban compared with standard of care (SOC) with the use of prophylactic low molecular weight heparin (LMWH) or unfractionated heparin (UFH) on a seven-category ordinal scale recommended by the WHO (Attachment 2) as a measure of clinical benefit at day 7 post randomization adjusted for baseline score in patients with moderate to severe COVID-19 (23-25).

[figure not shown]
The secondary objectives are to assess the efficacy and safety of rivaroxaban compared with standard of care (SOC) with the use of prophylactic low molecular weight heparin (LMWH) or unfractionated heparin (UFH) in the prevention of thromboembolic events, cardiovascular events, all-cause death or progression to intubation and invasive ventilation up to day 35 in patients with moderate to severe COVID-19.

The principal safety endpoint is fatal or non-fatal major bleeding as defined according to the ISTH classification.

Independent of the antithrombotic therapy, it should be stressed that all study patients will receive SOC with regard to COVID-19 specific therapies, such as anti-viral drugs, e.g. remdesivir or others, if clinically necessary.

An Executive Committee (EC), a Data Safety Monitoring Board (DSMB) and a Clinical Event Committee (CEC) will be commissioned for this study.

Figure 1 outlines the study design.

